1.3 STUDY RATIONALE AND BENEFIT–RISK ASSESSMENT

This Phase IIa cough profiling study will be conducted to evaluate potential inhibition of cough by GDC-6599, a small molecule inhibitor of TRPA1, and its effects on mannitol-induced cough and airway hypersensitivity in a subset of patients with CRC with asthma or UCC. The effects of GDC-6599 on cough and airway inflammation will also be assessed in a subgroup of patients with CRC who have a history of COPD.

The rationale for targeting TRPA1 for the treatment of chronic cough, asthma, and COPD is driven by the potential role of TRPA1 in contributing to airway smooth muscle contraction, sensory hypersensitivity, and neurogenic inflammation, which may lead to bronchoconstriction, AHR, and symptoms such as cough. Anticipated beneficial effects of targeting TRPA1 with GDC-6599 include reduction in bronchoconstriction and cough hypersensitivity in asthma and COPD and a reduction of cough hypersensitivity-associated CRC with asthma or UCC.

GDC-6599 *has been tested* in healthy volunteers in a completed Phase Ia/b SAD/MAD Study GA43010. No prior clinical experience with GDC-6599 exists in patients. The rationale for conducting the current study in patients with chronic cough is to evaluate the efficacy, safety, pharmacokinetics, and organ-specific pharmacodynamics (target inhibition in lung) in a relevant patient population.

An assessment has been conducted to determine whether the coronavirus disease 2019 (COVID-19) pandemic has any impact on the benefit-risk assessment of this study including, but not limited to, the patient population under study and study treatment. Review of the summary safety data generated in the initial *six dosing cohorts* of the SAD portion and three cohorts of the MAD portion of the Phase Ia/b SAD/MAD study GA43010 of the potent TRPA1-inhibitor GDC-6599 suggests that inhibition of the TRPA1 receptor is not associated with a higher frequency of infections or clinically significant findings in hematology parameters. Combined with further review of the toxicology data and the mechanism of action of GDC-6599, no impact is anticipated. The safety monitoring and management guidelines and risk mitigation measures provided in the study are considered adequate.

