24-hour OCC=objective cough count over 24 hours; AHR=airway hyperresponsiveness, expressed as RDR (calculated as maximum percent decrease in FEV₁ [relative to baseline of mannitol challenge] after the last dose of mannitol divided by cumulative dose of mannitol, and PD15 (defined as provoking dose of mannitol that induces a 15% decrease in FEV₁); CDR=coughs-per-dose ratio, calculated as total number of provoked coughs divided by cumulative dose of mannitol and expressed as coughs per 100 mg of mannitol; CRC=chronic refractory cough; DAIDS=Division of AIDS; FEV₁=forced expiratory volume in 1 second; NRS=Numeric Response Scale; PK=pharmacokinetic; RDR=response-dose ratio; UCC=unexplained chronic cough; TRP=transient receptor potential; TRPA1=TRP ankyrin 1; VAS=visual analog scale.

^a Adverse events will be graded according to the DAIDS Table for Grading the Severity of Adult and Pediatric Adverse Events (HSS 2017), with slight modifications for clarity and for alignment with internal practices (see Section 5.3.3 and [Appendix 10](#)).

Table 1 Objectives and Corresponding Endpoints (cont.)

Exploratory Objectives (cont.)	Corresponding Endpoints (cont.)

 To evaluate mannitol-induced airway smooth muscle hyper-responsiveness as a measure of TRPA1 airway activity and treatment benefit of GDC-6599, compared with placebo, in patients with CRC with asthma or UCC 	
 Change in mannitol-induced AHR from baseline to Day 14

 To evaluate the efficacy of GDC-6599, as compared with placebo, across each chronic cough disease subgroup 	
 Change in 24-hour OCC collected using the VitaloJAK cough recorder from baseline to Day 14 [REDACTED] Change in FEV_1 from baseline to Day 14 [REDACTED] Change in the severity of cough, as assessed through the use of the patient-reported cough severity VAS score, from baseline to Day 14 Change in the severity of cough, as assessed through the use of the patient-reported cough severity NRS score, from baseline to Day 14 [REDACTED]

 To evaluate cough hypersensitivity and AHR to mannitol across chronic cough disease subgroups 	
 CDR to mannitol across patients with different background diseases AHR to mannitol across patients with different background diseases

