This is relevant for TRPA1 antagonist because the TRPA1 receptor is sensitive to changes in osmolarity (Zhang et al. 2008) and blocking TRPA1 has shown to be reduce inflammation and bronchoconstriction in nonclinical models (Balestrini et al. 2021).

This study will test whether mannitol-induced AHR and cough are TRPA1 dependent and will explore mannitol-induced AHR and cough in different respiratory disease subsets. If mannitol is a TRPA1-responsive challenge agent, it may have utility in future clinical studies as a PD biomarker of TRPA1 activity. Furthermore, this study will instigate the relationship of baseline cough hypersensitivity, measured by mannitol-induced cough, with efficacy endpoints (e.g., 24-hour cough count) and inform the use of mannitol-induced AHR or cough as prognostic biomarkers for a personalized approach to treatment with a TRPA1-specific therapy such as GDC-6599.

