4.5.5 Mannitol Challenge Test

The mannitol challenge test is a commercially approved bronchial challenge test kit containing pre-filled mannitol capsules and a handheld dry powder inhaler device. During a mannitol challenge test, patients will orally inhale increasing doses of mannitol. After each dose, airway parameters will be measured by spirometry. Inhalation of mannitol doses will continue until all doses (cumulative 635 mg) are inhaled, *there is a ≥15% decrease in FEV₁ relative to baseline, or there is a ≥10% decrease in FEV₁ between two successive doses. The mannitol challenge test is required at Study Visit 1 (screening) and optional at Study Visits 4 and 7 (see Section 4.5.14).* Details regarding conduct of mannitol challenge are provided in the mannitol challenge test guidance.

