For sampling procedures, storage conditions, and shipment instructions, see the laboratory manual.

Blood samples collected for WGS or WES are to be stored until they are no longer needed or until they are exhausted. However, the storage period will be in accordance with the IRB/EC-approved Informed Consent Form and applicable laws (e.g., health authority requirements).

Refer to Section 4.5.10 for details on use of samples after patient withdrawal and confidentiality standards for data.

Data generated from blood samples collected for WGS or WES will be analyzed in aggregate rather than on an individual patient basis. Thus, there will be no identification and reporting of incidental findings to investigators or patients.

If permitted by local law, a patient may request access to uninterpreted WGS or WES data derived from analysis of his or her blood sample. If a patient wishes to access these data, the investigator must inform the Sponsor, using the following email address: [contact]. The Sponsor will provide available data to the investigator in the form of a raw genomic sequencing data file, but will not provide any interpretation of the data. The investigator should not include the data file in the patient's medical record. Samples may be stored and analyzed in the future, and some samples may never be analyzed. Thus, data may not be available at the time of the request or may never be available.

The aggregate results of any conducted research will be available in accordance with the effective Sponsor policy on study data publication.

4.5.14 *Optional Mannitol Challenge Tests*

Consenting patients will undergo optional mannitol challenge tests during each treatment period at Study Visits 4 and 7. Each mannitol challenge test is to be performed at least 2.5 hours after study drug administration. Details on the mannitol challenge test are provided in Section 4.5.5 and in the mannitol challenge test guidance. See Section 4.5.6 for details on cough monitoring during the challenges. Medication restrictions prior to the mannitol challenge are provided in Section 4.4.4.

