- t Details on the mannitol challenge test are provided in Section 4.5.5 and in the mannitol challenge test guidance. Medication restrictions prior to the mannitol challenge are provided in Section 4.4.4. If the optional mannitol challenge test is performed at Visit 4 and/or 7, it is to be performed at least 2.5 hours after study drug administration.

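### When a mannitol challenge ends on an FEV₁ criterion, the CDR denominator is itself an airway response, so bronchoprotection alone can shift CDR in either direction, and no visible analysis separates this from an effect on cough

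*Combined protocol and SAP*

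**What the plan says.** The Table 1 footnote in Section 2 defines CDR as "calculated as total number of provoked coughs divided by cumulative dose of mannitol", expressed per 100 mg. Its change from baseline to Day 14 is an exploratory endpoint, compared with placebo. Airway hyperresponsiveness (AHR), expressed as the response-dose ratio (RDR) and PD15, is a separate exploratory endpoint from the same challenge.

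Section 4.5.5 sets when the challenge ends: "Inhalation of mannitol doses will continue until all doses (cumulative 635 mg) are inhaled", or when "there is a ≥15% decrease in FEV₁ relative to baseline, or there is a ≥10% decrease in FEV₁ between two successive doses". It also states: "After each dose, airway parameters will be measured by spirometry".

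On what the drug should do, the anticipated effects in Section 1.3 "include reduction in bronchoconstriction and cough hypersensitivity in asthma and COPD". On the purpose of the challenge, Section 3.3.5 says: "This study will test whether mannitol-induced AHR and cough are TRPA1 dependent".

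The test is required at screening and optional at Visits 4 and 7. Section 4.5.14 says: "Consenting patients will undergo optional mannitol challenge tests during each treatment period at Study Visits 4 and 7". Footnote t of Appendix 1 sets its timing with the words "If the optional mannitol challenge test is performed at Visit 4 and/or 7".

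Section 6.4 plans descriptive summaries and no formal testing. The readable text contains no cough count at a matched dose, no adjustment for the dose reached, and no summary by reason for stopping.

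**The concern.** CDR is meant to measure cough, but in a patient stopped on FEV₁ its denominator is set by bronchoconstriction. If GDC-6599 protects the airway, that patient inhales more mannitol on drug, and coughs per 100 mg are averaged over a longer challenge reaching higher doses. Unless coughs rise exactly in proportion to cumulative dose, the ratio moves even though the patient coughs just as much at every dose as before.

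The plan wants to learn whether AHR and cough each depend on TRPA1, and Section 3.3.5 looks ahead to using the mannitol test as a pharmacodynamic or prognostic biomarker. A fall in CDR caused by the stopping dose could be taken for reduced cough sensitivity. A rise from the same cause could hide a real reduction.

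**Working it through.** The plan has no figure to reproduce. Section 6.1 gives 20 to 30 patients per cohort without inputs, and no CDR effect is stated. The check is algebraic.

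**Inputs from the documents.** CDR = 100 × C/D, where C is total coughs and D the cumulative dose (Section 2). The maximum D is 635 mg, with the FEV₁ criteria as above (Section 4.5.5). Section 3.3.5 says only that cough increases with dose; it does not give the shape.

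**Assumptions.** These are the curve exponent b, the dose D1 at which an FEV₁ stop occurs on placebo (the dose steps are not in the documents), and the share f of patients so stopped. Each is varied over a range.

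**Step 1: one patient, cough-dose curve unchanged by drug.** Let C = a × D^b. Then CDR = 100 × a × D^(b−1), and the drug/placebo ratio is (D2/D1)^(b−1). With D2 = 2 × D1:
- b = 0.5: 2^(−0.5) = 0.71, a change of −29%
- b = 1: 2^0 = 1, no change
- b = 1.25: 2^0.25 = 1.19, a change of +19%

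**Step 2: stopped at D1 on placebo, reaches 635 mg on drug.** The ratio is (635/D1)^(b−1).

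| b | D1 = 150 mg | D1 = 300 mg | D1 = 450 mg | D1 = 635 mg |
|---|---|---|---|---|
| 0.5 | 0.486 | 0.687 | 0.842 | 1.000 |
| 0.75 | 0.697 | 0.829 | 0.918 | 1.000 |
| 1 | 1.000 | 1.000 | 1.000 | 1.000 |
| 1.25 | 1.434 | 1.206 | 1.090 | 1.000 |

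The last column is the patient who reaches 635 mg in both tests and has no artefact.

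**Step 3: another shape.** Section 3.3.5 lists mechanical stimulation by dry powder among the causes of cough. If that adds a fixed 10 coughs to a slope of 0.10 coughs per mg, a 300 mg stop gives 100 × (10 + 30)/300 = 13.3 and the full test gives 100 × (10 + 63.5)/635 = 11.6, a ratio of 0.868.

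**Step 4: group level.** Suppose a share f stops at 300 mg on placebo, everyone else reaches 635 mg on placebo, and all reach 635 mg on drug. The geometric mean ratio is [(635/300)^(b−1)]^f.

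| b | f = 10% | f = 30% | f = 50% |
|---|---|---|---|
| 0.5 | 0.963 | 0.894 | 0.829 |
| 1 | 1.000 | 1.000 | 1.000 |
| 1.25 | 1.019 | 1.058 | 1.098 |

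**Step 5: dose-matched count.** Count coughs only up to the highest cumulative dose reached in both tests, Dc. If the curve is unchanged, C(Dc) is the same in both periods and the ratio is exactly 1 for any shape.

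**The case against.** The strongest case on the other side has five parts.

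- **The direction is not known.** A reader might infer that bronchoprotection will lower CDR. The documents do not support that: the shift is zero at b = 1 and reverses above it. This objection stands.
- **Most of the effect may be absent.** The FEV₁ rule fixes the dose only in patients who meet it, and their number is not given. At f = 10% and b = 0.5 the group ratio is 0.963. This stands.
- **AHR and cough are not inseparable.** A reader might conclude that the study cannot tell them apart. PD15 and FEV₁ after every dose come from the same challenge, so a dose-matched count or a breakdown by stopping reason is feasible if coughs are recorded by step. What remains is that no such analysis is visible. RDR does not fill the gap, because it shares CDR's denominator: a 15% fall is 5.0 per 100 mg at 300 mg and 2.36 at 635 mg.
- **Bronchoconstriction is itself a listed cause of mannitol cough (Section 3.3.5).** Bronchoprotection may truly reduce cough, and that is mechanism, not artefact. This stands and limits what any dose-matched count can show.
- **The stakes are limited.** The endpoint is exploratory, the on-treatment test is optional and the analysis is descriptive. The challenge guidance is not among the documents and some exploratory objectives are blacked out, so relevant detail may exist elsewhere. This stands.

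A reader might also suspect that selecting patients on a screening CDR of at least 12 biases the treatment effect through regression to the mean. In patients tested in both periods, the single screening baseline is subtracted from both values and cancels in the drug-placebo contrast.

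On footnote t, the and/or wording may only allow for a missed or declined test. Even so, a patient tested in one period supplies no within-patient contrast.

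**Conclusion.** The point holds in a limited form. In FEV₁-stopped patients the CDR denominator is an airway outcome that the sponsor anticipates the drug may improve, so CDR can shift with the cough-dose curve unchanged. In an affected patient whose dose doubles, the shift runs from −29% (b = 0.5) through zero (b = 1) to +19% (b = 1.25). In the group illustrations for a 300 mg placebo stop it runs from a ratio of 0.829 to 1.098. These figures rest on an assumed power curve, assumed stopping doses and an assumed share stopped. They show the possible scale and do not predict the trial's result.

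No visible analysis separates this shift from an effect on cough, although Section 3.3.5 sets out to examine both. Severity is low: the primary endpoint, the 24-hour cough count, is unaffected.

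**What to change.** Keep CDR as defined. In Section 6.4, or in a separate analysis plan, add two items:

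1. For patients tested at both Visit 4 and Visit 7, a within-patient drug-versus-placebo comparison, on the log scale, of coughs up to the highest cumulative dose reached in both tests. State in advance how zero counts are handled.
2. CDR reported by reason for stopping (635 mg reached, each FEV₁ criterion, other), by treatment period.

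Record coughs by dose step if the challenge guidance does not already require it. Reconcile footnote t of Appendix 1 with Section 4.5.14 on whether a consenting patient is tested in one period or in both.

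The cost is analysis wording and, if needed, one more column on the counting sheet, since coughs are already counted by hand. The downsides are that coughs above the common dose drop out of the added comparison, and that it does not remove the pathway in which bronchoconstriction itself provokes cough. The breakdown by stopping reason groups patients by a post-treatment outcome, so it is supportive only.

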3. STUDY DESIGN

3.1 DESCRIPTION OF THE STUDY

3.1.1 Overview of Study (Part A and Part B)

This Phase IIa, multicenter, randomized, double-blind, placebo-controlled, crossover study is designed to evaluate the efficacy, safety, pharmacokinetics, and PD effects of GDC-6599 across *three* cohorts in patients with chronic cough. In the main study (Part A), approximately 60 patients with chronic cough will be enrolled across *two* cohorts: CRC with asthma *with or without* atopy (n=approximately 30), and UCC

(n=approximately 30). In the substudy (Part B), approximately an additional 20 patients with a diagnosis of CRC with COPD *with or without chronic bronchitis* (CRC COPD±CB) despite standard-of-care treatment *will be enrolled*.

The study will consist of a screening period of approximately 21 days, followed by a 14-day treatment period. After a 14-day washout, patients will begin another 14-day treatment period during which time the opposite treatment will be administered. A 14-day washout period and [REDACTED] safety follow-up period will follow.

Patients who meet all eligibility criteria (see Section 4.1) will be randomized in a 1:1 ratio to receive [REDACTED] mg GDC-6599 or placebo [REDACTED] [REDACTED] [REDACTED] for 14 days during the first study period (Treatment Period 1, Study Visits 2–4). Following a 14-day washout period, patients will cross over to the second study period (Treatment Period 2, Study Visits 5–7) and will receive the alternate treatment ([REDACTED] mg GDC-6599 or placebo) [REDACTED] for 14 days starting at Study Visit 5.

VitaloJAK® cough recorder (Vitalograph Inc., Maids Moreton, U.K.) will be used to monitor spontaneous cough frequency *at screening and throughout the study*. [REDACTED]

To characterize the pharmacokinetic (PK) properties of GDC-6599, blood samples will be taken at various timepoints before and after dosing.

[figure not shown]
To characterize the PD effects of GDC-6599, [REDACTED]

[REDACTED] [*collected under prior versions of this protocol*] will be collected at timepoints indicated in [REDACTED]

A safety follow-up assessment (Study Visit 8) will be scheduled [REDACTED] after the last dose of study treatment to ensure patient safety.

At applicable sites, certain study assessments may be performed by a trained nursing professional at the patient's home or another suitable location, if the patient has given written informed consent to participate in mobile nursing (MN) visits and mobile nursing is available.

[Figure 1](#) presents an overview of the study design. A schedule of activities is provided in [Appendix 1](#).

Patients who are not able to complete the assessments or are unable to meet eligibility requirements during the screening period (screen failure) will be permitted to be re-screened once (for a total of two screenings per patient) at the investigator's discretion. Patients who re-screen \leq 6 weeks after Informed Consent Form completion must repeat the assessments that triggered the screen failure. Patients who re-screen $>$ 6 weeks after Informed Consent Form completion are required to repeat the consent process and all assessments. The investigator will maintain a record of reasons for screen failure (see Section 4.5.1).

3.1.2 Internal Monitoring Committee

An Internal Monitoring Committee (IMC) will monitor patient safety throughout the study. Members from the IMC will be unblinded to treatment assignment and include representatives from clinical science, clinical safety, and biostatistics from the Sponsor. The IMC may invite representatives from other functional areas (e.g., clinical pharmacology) or external experts on an ad hoc basis when additional expertise is required. Further details regarding roles and responsibilities will be outlined in the IMC Charter.

Periodic safety reviews of cumulative data will be performed by the Sponsor's IMC as outlined in the IMC Charter. Ad hoc meetings may be held at the request of the IMC or Sponsor at any time to address potential safety concerns. The data to be reviewed will include, but will not be limited to, demographics, concomitant medications, study drug administration, adverse events, serious adverse events, adverse events of special interest, ECGs, and relevant laboratory results.

At the time of each review, the IMC *may* make recommendations *such as the following*: the trial continues as planned, the trial is stopped for safety reasons, the dose *level or frequency is changed*, additional analyses need to be performed, or enrollment will be held pending further safety evaluations. *The IMC may also provide recommendations on amending the protocol.* Decisions will be made in consideration of the totality of the available data. Final decisions will rest with the Sponsor's study team.

A detailed description of the procedures, data flow, and meeting schedule of the IMC will be provided in the IMC Charter.

3.2 END OF STUDY AND LENGTH OF STUDY

The end of this study is defined as the date when the last patient, last visit occurs or the date at which the last data point required for statistical analysis or safety follow-up is received from the last patient, whichever occurs later. Each patient is expected to remain in the study for a maximum of approximately 12 weeks. The end of the study is expected to occur approximately 12 weeks after the last patient is enrolled.

In addition, the Sponsor may decide to terminate the study at any time.

The total length of the study, from screening of the first patient to the end of the study, is expected to be approximately 18 months.

3.3 RATIONALE FOR STUDY DESIGN

3.3.1 Rationale for Patient Population

Three cohorts of chronic cough patients with different disease backgrounds (CRC asthma *with or without atopy*, UCC, or CRC COPD) will be enrolled in this study to assess the potential heterogeneity of *treatment effects on cough frequency across disease backgrounds*. *The study will also explore potential heterogeneity of baseline cough hypersensitivity to inhaled mannitol and the relationship with baseline cough frequency.*

Cough is an important symptom of chronic lung disorders and is often cited by patients with CRC with asthma, CRC with COPD, or idiopathic pulmonary fibrosis as the most bothersome of respiratory symptoms having an adverse impact on HRQoL (Polley et al. 2008) and is a key aspect of disease burden and control (Marsden et al. 2016). Despite the high unmet need, there are currently no approved drugs for the treatment of CRC with asthma, UCC, or CRC with COPD.

Chronic cough, despite adherence to guideline-based standard-of-care treatment, represents high unmet medical need in patients with CRC with asthma, UCC, or CRC with COPD. Cough hypersensitivity to inhaled irritants is a key feature of chronic cough. This study will target patients with CRC with atopic asthma, CRC with non-atopic asthma, UCC, and CRC COPD. Patients must have a diagnosis of chronic cough based upon consensus guidelines (American College of Chest Physicians [CHEST] 2018;

European Respiratory Society [ERS] 2020). A mannitol CDR of at least 12 coughs/100 mg is required for inclusion in this study (see Section 4.1.1) in order to identify patients with cough hypersensitivity and avoid including patients with very low mannitol-evoked cough responses, in whom a treatment effect would be difficult to demonstrate.

Heightened and exaggerated cough responses to tussive stimuli is recognized as a unifying feature of patients with chronic cough (Hilton et al. 2013; Canning et al. 2014). However, in the clinical setting, it is clear that the processes regulating cough are heterogeneous across different patient subgroups. Disease-specific profiles of neuronal sensitivity have been demonstrated in the cough responses to inhaled tussive stimuli in patients with COPD, healthy smokers, CRC, asthma, compared with healthy volunteers (Belvisi et al. 2016). The extent to which this may be a consequence of increased activation of vagal afferents by pathology in the airways (e.g., inflammatory mediators, excessive mucus) or an altered neuronal phenotype is unknown. There is recent evidence illustrating distinct patterns of neuronal dysfunction within subsets of UCC patients. A recent study has identified four phenotypes of cough hypersensitivity in patients with UCC based upon activation of the TRPA1 and TRPV1 channels using selective agonists (Long et al. 2019). Data from two recent studies assessing cough hypersensitivity to capsaicin, a TRPV1-specific irritant, in asthma patients suggest that heightened sensitivity to inhaled capsaicin in non-atopic asthma patients relative to atopic patients reflects greater neuronal dysfunction associated with poor asthma control and worse outcomes. (Satia et al. 2017; Kanemitsu et al. 2020). This supports the existence of heterogeneity in cough pathways and an approach for developing personalized anti-tussive therapies.

Understanding the basis for this heterogeneity is key to the development of personalized treatments for cough. This study is designed to profile cough hypersensitivity to inhaled mannitol and the relationship to cough frequency and cough severity across *four distinct subsets* of patients with chronic cough (CRC with atopic asthma, CRC with non-atopic asthma, UCC, and CRC COPD). Treatment with GDC-6599 and placebo across two treatment periods will inform the relative contribution of TRPA1 airway activity to the cough profiles.

